Method: Patients will be recruited across secondary services in North West England and will be randomised (using SealedEnvelope.com) to Actissist + TAU (n=85) or ClinTouch + TAU (n=85) who will use the software 6 days/week for 12-weeks alongside TAU. Participants will receive training in using the software, which will be pre-loaded on a loaned Smartphone or downloaded on a participant's own Smartphone. A researcher will also help participants set treatment goals at the software training session so that participants can work towards a pre-specified goal throughout the intervention period. At end of treatment, 12-weeks post-randomisation and 24-weeks post-randomisation, a researcher blind to group allocation will collect outcome data (e.g. symptoms, functioning, quality of life, empowerment), which will be managed on a statistical database. Clinical participants will be reimbursed (£20) at each assessment point and for any qualitative interviews they take part in. The project officer or another member of the research team will phone, text or email (depending on participant preference) participants at weeks 1, 2, 4, and 8 to check the app is working smoothly and remind participants to charge the device, alert the participant to the receipt of the mARM survey (in weeks 4 and 8), and in week 11 to establish a date for the researcher conducting the follow up assessments. Safety concerns will be managed in close consultation with care co-ordinators. Qualitative interviews will be conducted with purposefully selected participants (n >20) after the 12 week post-randomisation assessment, and with around 15 Trust staff whose client's participated in the trial to explore acceptability and usability of Actissist 2.0. Over a 19-month recruitment period, 170 consenting early intervention psychosis patients recruited from NHS Trusts across the North West of England who express an interest and are able to give informed consent will be randomised to TAU plus Actissist (N=85) or TAU plus ClinTouch (N=85). Randomisation will be conducted using an independent online randomisation tool (www.sealedenvelope.com), according to a standard operating procedure developed by [name], the project statistician.

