Objectives: complete data analysis; dissemination will occur as detailed in the communications plan (attached); develop a strategic plan encompassing an analysis of the regulatory requirements for CE Mark and IP position, and review of potential partners/licensees to market. Commercial opportunities for Actissist will include a comprehensive analysis and monitoring of the prior art throughout the project's duration, development of an appropriate IP strategy and, if necessary, a preliminary assessment of freedom to operate. Market research identifying market needs for this technology and possible business models for commercial exploitation will be conducted.

Sample size calculation.

Phase 1: Involves approx. 5 staff members of either a local NHS Trust or University of Manchester to beta-test the Actissist app for 7 days and provide feedback on the usability and functionality of the app.

Phase 2: 170 participants recruited over 19 months. 63 per group will have 80% power to detect an effect size of 0.4 (6 points on the PANSS with an SD of 15), based on a two-group t-test with a 0.05 two-sided significance level, assuming a baseline-endpoint correlation of 0.6. Allowing 20% loss to follow-up, in order to maintain 80% power we will recruit 85 patients per group (N=170). The SD, correlation and attrition rate are based on figures from Actissist 1.0. Randomisation will be 1:1, and stratified by service (early intervention vs community mental health).

Service user ehealth and mHealth Interest Survey (EMIS). We anticipate recruiting upwards of 300 participants (including 170 full trial participants) to complete the EMIS in order to obtain a representative sample.

eHealth and mHealth Interest Survey (EMIS-CV). We anticipate recruiting upwards of 300 participants to complete the EMIS-CV in order to obtain a representative sample.

Qualitative interviews with non-participants/early withdrawers. Individuals who decide not to participate, or who withdraw early from the intervention, will be invited for a one-off interview to explore their reasons for not participating. It is not possible to accurately predict the number of service users who decide to participate in this phase; however, we expect a minimum number of 5 participants.

Phase 3: N/A

Therefore, in total, we expect the sample size of the overall project to be N=605 (170 trial plus EMIS; 130 EMIS-only); 300 EMIS-CV; 5 non-participant/early withdrawal interviews).

Inclusion criteria.

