5.0 Data collection, management and analysis

Data Collection Methods

All outcome measures will be administered at baseline and subsequently at 12 weeks and 24 weeks post-randomisation by RAs who will have been trained in the use of all the instruments and scales, to achieve a satisfactory level of inter-rater reliability. Accuracy in administering and scoring the PANSS at baseline and at the 12 and 24 week follow up stage is critical in order to detect any change that might be attributable to the app the participant used. To ensure that important details aren't missed, the PANSS assessments will be digitally recorded using an encrypted device to enable our research team to review participants' responses when scoring the assessment. Recordings will be downloaded to a secure server on return to the office and deleted at the end of the study once reliability of rating has been assured. Regular training sessions including the use of role play will be conducted with all research assistants in order to maintain reliability and prevent rater drift. Participants will be offered choices regarding length of assessments, including the option of breaks and multiple occasions. The option to conduct the PANSS assessment over the telephone at 12 and 24 weeks post-randomisation will be offered to participants whose circumstances may have changed since baseline assessment, e.g., they are now working. Assessment measures will be clearly prioritised so that the most important will be collected first to avoid missing data. We will have a standard protocol for managing any distress that is associated with the completion of measures, which we have successfully utilised in several trials and has been developed in collaboration with service users (Appendix 1).

Note: for participants recruited to Actissist, who give written consent for their most recent PANSS, and other questionnaire data collected at final follow up in their previous study that is common to the Actissist baseline to be shared by their previous study team, the time taken for the completion of the baseline measures will be substantially reduced.

Protection Against Bias

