Our assessment of the primary outcome will be blinded. Blindness of raters is ensured using a variety of procedures, including briefing participants prior to assessment not to disclose their allocation and data protection of randomisation information. RAs will remain blind to group allocation. An RA who did not conduct the phone set up session will conduct the follow up assessment to maintain the blind. The project officer, or a member of the research team independent to the follow up procedure, will book follow up appointments to further ensure blinding is maintained. Unblindings will be regularly monitored and recorded. Deliberate unblinding would only occur in the case of a serious adverse incident such as risk towards self/others by a participant. The statistician will be blinded during the analysis by withholding the identity of the randomised groups and only once the analysis is completed and interpreted will these be revealed. Due to the nature of the intervention, all participants will be unblinded and fully aware of their allocation to the intervention or control groups.

Randomisation Process

The randomisation process will be conducted by a remote internet based randomisation service (www.sealedenvelope.com). The allocation sequence will be developed using a computer random number generator to allocate participants on a 1:1 ratio, stratified by service (early intervention vs community mental health).

Once the eligibility of a patient has been confirmed and informed consent has been obtained, the researcher will assign a unique identification number to the patient and send this to the project manager. Having accessed the randomisation website, the project officer will enter only the identification number into the randomisation service, submit this information, and the next treatment allocation will be revealed on screen. Participants will then be informed of their allocation status. An email confirmation of the identification number, the allocated treatment and the date and time of randomisation is sent to the project officer. We have previous experience of using web-based randomisation in this setting, and do not anticipate any practical issues arising in this study. The randomisation list will be kept by the remote randomisation service (www.sealedenvelope.com), and kept separate to the collection of outcomes on the study database. The randomisation list will only be revealed to the researchers once all the recruitment is completed.

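### The randomisation list may be released to the researchers when recruitment ends, up to 24 weeks before blinded PANSS rating ends, and nothing exempts the raters

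*Protocol*

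**What the plan says.** All passages are in the protocol.

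- **Release of the list** (section 5.0, Randomisation Process): "The randomisation list will only be revealed to the researchers once all the recruitment is completed".
- **Timing and raters** (section 5.0, Data Collection Methods): "All outcome measures will be administered at baseline and subsequently at 12 weeks and 24 weeks post-randomisation by RAs".
- **Who the assessor is** (section 2.0, Method): at the 12- and 24-week assessments "a researcher blind to group allocation will collect outcome data".
- **Blinding commitment** (section 5.0, Protection Against Bias): "RAs will remain blind to group allocation", with no end date. The same subsection lists protection of the randomisation information among its safeguards and confines deliberate unblinding to serious adverse incidents. It has follow-up done by an RA who did not run that participant's phone set-up, and states that participants know their allocation.
- **Statistician** (same subsection): group identities are withheld, and "only once the analysis is completed and interpreted will these be revealed".
- **Link between list and forms** (section 5.0, Randomisation Process and Data Management): randomisation is by identification number, and each participant's trial number is written on every assessment form.
- **Accrual** (section 2.0, Sample size calculation): "170 participants recruited over 19 months", with 20% loss to follow-up allowed for.

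**The concern.** Withholding the list until recruitment closes protects allocation concealment: nobody can foresee the next assignment. It does not protect outcome assessment, which runs on until the last participant's 24-week visit. Everyone randomised in the final 24 weeks of recruitment still has at least one PANSS rating to come when the list may be opened. Because the list is keyed to the number on the assessment forms, anyone holding it can read off the arm.

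The primary outcome, PANSS total score, is scored from an interview by a member of the research team, and participants are not blinded. A rater who knows the arm can, without intending to, score in favour of the new app. Staff who followed the release sentence as written would break no instruction in that sentence, yet would defeat the blinding commitment in the preceding subsection.

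**Working it through.** **1. Does the release reach the raters?**

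- The term 'researchers' is not defined. Section 2.0 uses 'researcher' for the blinded person who collects outcome data, so on a plain reading the raters are included.
- The project officer performs each randomisation and receives the allocation by email. Revealing the list therefore adds nothing for that role; it matters for staff who do not already know the arms.
- No sentence exempts the rating RAs.

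**2. Is it consistent with the other blinding text?** Release to all researchers at the end of recruitment does not fit RAs staying blind without time limit. Nor does it fit deliberate unblinding being confined to serious adverse incidents. These are the sentences in conflict.

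**3. How many ratings are exposed?** The protocol gives no figure for ratings outstanding at the close of recruitment, so there is none to reproduce.

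Inputs: N = 170; recruitment 19 months; visits at 12 and 24 weeks; 20% loss (all from the protocol). Uniform accrual is an assumption.

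- Recruitment length: W = 19 × 30.4375 / 7 = 82.6 weeks.
- Share outstanding at close, uniform accrual: f / W for a visit at f weeks.
- Number expected to be assessed after loss: 170 × 0.80 = 136.

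| Visit | Share outstanding | Of 170 | Of 136 after loss |
|---|---|---|---|
| 12 weeks | 12 / 82.6 = 14.5% | 24.7, about 25 | 19.8, about 20 |
| 24 weeks | 24 / 82.6 = 29.1% | 49.4, about 49 | 39.5, about 40 |

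**4. How far does this depend on accrual?** Two extremes bracket it:

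- Rate rising linearly from zero: 1 − ((W − f)/W)². This gives 26.9% at 12 weeks and 49.7% at 24 weeks.
- Rate falling linearly to zero: (f/W)². This gives 2.1% at 12 weeks and 8.4% at 24 weeks.

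The range is about 2–27% at 12 weeks and 8–50% at 24 weeks.

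**5. What could that do to the result?** Suppose knowing the arm shifted the between-arm difference by 3 points in the exposed ratings. This is purely an assumption, half the 6-point target difference. The overall shift is share × 3:

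- 12 weeks: 0.145 × 3 = 0.4 points (range 0.021 × 3 = 0.1 to 0.269 × 3 = 0.8).
- 24 weeks: 0.291 × 3 = 0.9 points (range 0.084 × 3 = 0.3 to 0.497 × 3 = 1.5).

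**6. Does a later trigger fit the timetable?** If recruitment starts at the beginning of month 6 (assumption), the last 24-week visit falls at 5 + 19 + 24/4.348 = 29.5 months. The RCT phase runs over months 6–33, so it fits.

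**The case against.** The strongest reply is that the release sentence sets an earliest time and does not instruct anyone to hand over the list. It sits under Randomisation Process, where its natural purpose is allocation concealment; rater blinding has its own subsection, which says without time limit that RAs stay blind. 'Researcher' is also used for the person who trains the participant at app set-up, and the protocol nowhere says that raters receive the list. All of this stands as far as it goes. It shows that the authors probably did not intend to unblind raters. It does not remove the conflict, because the sentence names the researchers without exception and the protocol does not say which passage prevails.

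A reader might infer that rater blinding is lost by rule for the last participants. The documents do not support that: unblinding is permitted, not required, and another sentence forbids it for RAs.

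A reader might also see a contradiction with the rule for the statistician. That rule concerns a different person and is compatible with others seeing the list sooner.

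Nor is blinded rating the only protection. The comparator is another app with matched alerts, PANSS interviews are recorded, raters are trained for reliability, and the statistician is blinded. Blinded rating is, however, the main safeguard against a rater's knowledge of the arm.

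Finally, the exposed share rests on an accrual pattern that the protocol does not give, and most ratings would be finished before release under uniform accrual (about 85% at 12 weeks and 71% at 24 weeks). The share is nevertheless above zero under every pattern examined.

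**Conclusion.** The point holds as an internal contradiction in section 5.0: the protocol permits the list to be shown to the researchers, raters not excepted, while blinded PANSS rating is still under way, and elsewhere in the section promises that RAs stay blind.

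Under uniform accrual about 14.5% of 12-week and 29% of 24-week ratings are exposed; the plausible ranges are about 2–27% and 8–50%. Ratings completed before release are not counted. The documents do not show that any rater would in fact be unblinded, and the possible shift in the treatment effect depends on an assumed rating bias. The case for change rests on an avoidable risk to the primary outcome that the text itself creates.

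**What to change.** Replace the release sentence with:

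*The randomisation list will not be revealed to the researchers, including all outcome-rating RAs, until the last 24-week assessment is complete and the database is locked; the project officer's and the TSC/DMEC's access is unchanged.*

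Naming the recipients matters. A blanket embargo would clash with section 7.0, which gives the TSC/DMEC unblinded comparative data as they accrue, and with the project officer's role in randomising. Keep the existing rule that the statistician stays blinded until the analysis is interpreted, and the existing provision for unblinding after a serious adverse incident.

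The cost is one protocol sentence and one instruction to the randomisation provider. No extra participants, staff or visits are needed, and the later trigger fits the stated RCT phase if recruitment starts in month 6.

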6.0 Statistical Analysis

Quantitative Data.

The quantitative data analysis will be carried out under the supervision of [name] at Kings College London. The study database is hosted on the University of Manchester's Health eResearch Centre secure server; authorised login from another university site for co-investigators is possible to remove the need for electronic transfer of data via email in password protected files. Our primary analysis will be by an intention-to-treat approach using all randomised participants and report data in line with the CONSORT 2010 Statement (Schultz et al., 2010) showing referral and attrition rates (i.e. participant flow). The primary outcome measure will be psychotic symptoms (PANSS Total Score) based on the fact that the Actissist app targets key psychosis domains and we observed a signal on PANSS total score post-treatment in our feasibility trial. Treatment effects on the primary and secondary outcomes will be estimated using standard linear regression models. No interim analysis is planned. Every effort will be made to follow up all participants in both arms for assessments, and the analysis will use, where appropriate, statistical techniques for handling missing data.

Data obtained from the EMIS and EMIS-CV will be analysed descriptively (i.e. mean scores and percentage rates of ownership and interest) by a clinical doctorate student. Additionally, the student will link trial participants' responses to the EMIS survey questionnaire to their app usage data during the intervention period and the change in their clinical outcome scores. Linking will be achieved using pseudonymised information, i.e., participants' unique study ID on the EMIS survey response form and ID on the Baseline/ 12 and 24 week time point follow up CRFs (and/or study databases for these time points) only. There will be no requirement to access files with participant identifiable information. The EMIS responses from non-trial participants and EMIS-CV responses from mental health care staff are obtained via online survey and are anonymous.

Trial participants' EMIS responses, app usage and change in clinical outcomes will be examined to understand service user smartphone and technology ownership and health app use and how this effects clinical outcomes in digital health interventions .Mental health professionals' use and confidence in using technology and smartphones and their engagement with apps for health management is explored in the clinician survey.

Qualitative data.

Qualitative data will be digitally recorded, transcribed by the research team, checked for accuracy and analysed using thematic analysis (Braun & Clarke, 2006) by the PI, research assistants and qualitative methodologist ([name]). We shall ask participants, as well as the ERG, to review and verify themes, usually referred to as 'member checking' or 'participant verification'. Additionally, clinical members of our research team ([name] and [name]) will rigorously review the research process. This 'peer verification' process (together with member checking) is a recognised method of ensuring 'trustworthiness' of the data and subsequent findings (Gibson & Brown, 2009). Records of field notes will be maintained and reflections providing adjunctive data will be used to illuminate and justify interpretative decisions. NVivo (2012) qualitative software package will be used to support data management and analysis.

7.0 Research Governance

Project Management Group (PMG)

Operational management and governance of the study and transitions between phases will be through the Actissist Project Management Committee (PMG) comprising who will ensure that the project is delivered according to the protocol and ethical guidelines. The PMG will meet monthly and consists of the following individuals:

- [name] (Principal Investigator)
- [name] (Research Assistant)
- [name] (Research Assistant)
- [name] (Research Assistant)
- [name] (Project Officer)
- [name] (Co-Investigator)
- [name] (Co-Investigator)
- [name] (Study Statistician)
- [name] (Technical Lead)

The PMG will report to the wider Investigator team on a three-monthly basis. A member from the University of Manchester Intellectual Property (UMIP) division will also be invited to

project meeting on a quarterly basis. A member from the Medical Research Council (MRC) will also be invited to attend PMG meetings as required in the funding guidelines and more regularly if necessary.

Combined Trial Steering Committee (TSC) and Data and Ethics Monitoring Committee (DMEC)

Although it is not a requirement, a joint TSC/DMEC will be established in the interest of best practice. The TSC/DMEC will have access to unblinded comparative data as it accrues and monitor these data, the quality of these data, monitor adverse events and make recommendations to the PMG on whether there are any ethical or safety issues on whether the study should continue. The TSC/DMEC will meet at the outset and then annually; although, additional meetings may be arranged if required. The TSC/DMEC will consist of the following individuals:

- Independent Chair ([name])
- Clinical representative ([name])
- Service user representative ([name])
- Independent statistician ([name])

Measuring Adverse Events

At each study visit, or as otherwise specified in the protocol, the PI (or delegate) is responsible for eliciting details of any adverse events (AEs) that may have occurred since the previous study visit and ensuring that these are evaluated appropriately. The Actissist research team will assess the 'relatedness' of an event in the first instance. Conclusions will be included in the event report, and this will be sent to the relevant recruiting R&I Departments (Greater Manchester Mental Health NHS Foundation Trust and Pennine Care NHS Foundation Trust) and to [name] (Independent TSC/DMEC Chair), who will also assess the 'relatedness' of an event and communicate their conclusions to the Actissist PMG. The PI will periodically (for example quarterly) perform and document a review of all adverse events occurring on the study, in order to identify any trends such as an increase in numbers or severity of events.

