A trained researcher will then meet with the potential participant at a time or place convenient for them to briefly ask about their experiences to identify whether the person is likely to meet the eligibility criteria. If the service user is suitable, they will be asked to consent to the study and complete the baseline assessment. After the participant has consented and completed the baseline assessment, a trained researcher will arrange to meet with the participant to take them through the app functions and to invite them to set some goals to work towards throughout the intervention period.

The Actissist software will emit a pseudo-random alert 3 times a day, 6 days a week over 12 weeks with branching items targeting key relapse factors in FEP (medication non-adherence, symptoms, socialisation, perceived criticism and substance misuse). Participants will choose either to use a loaned smartphone which is pre-loaded with the app or the researcher may download the application onto their own handset. For those participants randomised to the ClinTouch (control) condition, for parity with the demands of the Actissist condition participant's will submit one and a half data points daily with 10 branching items covering

positive psychotic symptoms, anxiety and mood as validated in a previously validated MRC study (PI: [name]). As each full data point is collected over two separate alerts, this equates to receiving three alerts every day. As with ACTISSIST, participants will choose either to use a loaned smartphone which is pre-loaded with the app or the researcher may download the application onto their own handset. Both the active and control condition apps will be used 6 days a week over 12 weeks.

In the unlikely event that a participant loses a smartphone, the participant will be provided with a replacement; if the participant loses the replacement smartphone, they will be offered one further replacement. If participants lose both replacements, they will not receive a further replacement smartphone; however, in this situation, participants would still be given the opportunity to take part in the follow-up assessments.

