A research assistant will train participants in how to use the software. Software will be pre-loaded on a loaned smartphone or downloaded on the participant's own smartphone. Safety concerns will be managed in close consultation with participants' care co-ordinators and emergency contacts are clearly available on both apps.

For both conditions, a trained research assistant will train participants in how to use the software. For both Actissist and ClinTouch, participants will view written 'in-app' instructions and a printed hard copy of instructions on how to use the app. Software will be pre-loaded on a loaned smartphone or downloaded on participant's own smartphone. The project officer will phone, text or email (depending on participant preference) all participants at weeks 1, 2 4, and 8 to check the app is working smoothly and remind participants to charge the device, alert the participant to the receipt of the mARM survey (in weeks 4 and 8), and in week 11 to book a date for follow-up assessments. Concerns will be managed in close consultation with participants' care co-ordinators and emergency contacts will be clearly available in the menu options on both apps.

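### Systematic adverse event enquiry happens only at study visits up to 12 weeks apart and does not use the contacts already scheduled during app use, so events may be captured late or incompletely

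*Protocol*

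**What the plan says.** Section 7.0 (Measuring Adverse Events) sets the timing of enquiry: "At each study visit, or as otherwise specified in the protocol", with the task being "eliciting details of any adverse events (AEs) that may have occurred since the previous study visit". No other time for adverse event enquiry is given anywhere in the protocol.

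Section 5.0 fixes the assessment visits: "All outcome measures will be administered at baseline and subsequently at 12 weeks and 24 weeks post-randomisation". Section 2.0 (Service user involvement) adds one meeting after baseline, at which "a trained researcher will arrange to meet with the participant to take them through the app functions". The exposure is the same in both arms: "Both the active and control condition apps will be used 6 days a week over 12 weeks".

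Section 4.0 schedules contacts by phone, text or email with "all participants at weeks 1, 2 4, and 8 to check the app is working smoothly". The same contacts carry a charging reminder and, at weeks 4 and 8, notice of the alliance survey. There is a further contact "in week 11 to book a date for follow-up assessments". The Method text in 2.0 describes the same schedule.

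Other safety provisions exist. Sections 2.0 and 4.0 say that concerns are handled with care co-ordinators, and both apps display emergency contacts. Appendix 1 requires action on risk disclosed in any session or contact, including by telephone.

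**The concern.** The app is self-guided and prompts people with current psychotic symptoms three times a day to work on matters such as paranoia and distressing voices. Plausible harms include worsening symptoms or distress provoked by the prompts. Many such events would not amount to a disclosure of risk, so they would come to light only if someone asked.

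As written, the first time anyone must ask about the period of app use is when that period ends. An event in week 1 could be elicited 11 weeks later. It could then miss one of the PI's periodic reviews, for which the protocol suggests a quarterly interval. The Introduction itself counts the reduction of recall bias over preceding weeks or months as an advantage of the app, yet adverse event collection relies on recall of that length.

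People who leave before week 12 are a second gap. They may include some who left because the app troubled them, so the missing reports need not be a random sample.

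**Working it through.** **Inputs**
- Enquiry points as written: the study visits (7.0). Assessments fall at weeks 0, 12 and 24 (5.0). The set-up meeting comes before app use begins and so does not divide the exposure (2.0).
- Exposure: 12 weeks in both arms (2.0).
- Scheduled contacts: weeks 1, 2, 4, 8 and 11, all participants (4.0).
- Expected loss to follow-up: 20% of 170 randomised, timing not stated (2.0, Sample size calculation).
- Assumption: contact weeks and visit weeks are counted on the same clock. The protocol counts visits from randomisation and does not say where the contact weeks start.

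**Step 1. Enquiry gaps as written.** Points at 0, 12 and 24 give gaps of 12 − 0 = 12 and 24 − 12 = 12 weeks. No enquiry point falls inside the exposure.

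**Step 2. Stated purpose of each contact.**

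| Week | Stated purpose | Adverse event question |
|---|---|---|
| 1, 2 | app function, charging | none stated |
| 4, 8 | app function, charging, alliance survey | none stated |
| 11 | booking the follow-up assessment | none stated |

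**Step 3. Enquiry gaps if the contacts were used.** Points at 0, 1, 2, 4, 8, 11, 12 and 24 give gaps of 1, 1, 2, 4, 3, 1 and 12 weeks. The longest gap during app use falls from 12 weeks to 4 (weeks 4 to 8). The gap from week 12 to week 24 is unchanged.

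**Step 4. People with no enquiry during app use.** The ceiling is 0.20 × 170 = 34. It is reached only if every loss occurs before week 12. Losses between weeks 12 and 24 would already have been asked about the app period.

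**Step 5. Size of under-capture.** The protocol gives neither an adverse event rate nor a recall figure, so this cannot be derived. The following illustration rests wholly on assumed values. Suppose that 20% of one arm and 40% of the other truly have an event, that a fraction c of them is captured equally in both arms, and that 85 per arm are compared at two-sided 0.05:

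power ≈ Φ( (p₂ − p₁) / √{[p₁(1 − p₁) + p₂(1 − p₂)] / 85} − 1.96 ), with p₁ = 0.20c and p₂ = 0.40c.

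For c = 0.6: p₁ = 0.12, p₂ = 0.24, standard error √(0.288 / 85) = 0.0582, z = 0.12 / 0.0582 = 2.06, power = Φ(0.10) = 54%.

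| c | 0.5 | 0.6 | 0.7 | 0.8 | 0.9 |
|---|---|---|---|---|---|
| power | 45% | 54% | 62% | 70% | 77% |

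Lower capture makes a real difference in harms harder to see, but by how much depends on the value chosen for c. The protocol sets out no hypothesis test on adverse events, and the illustration ignores dropout. The conclusion does not rest on it.

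**The case against.** The strongest reply is that the protocol contains no error here. Its rule is explicit, each enquiry reaches back to the previous visit, and so the whole period of app use is asked about. Asking more often is a preference. That stands in part: there is no contradiction and no wrong figure. What remains is that all of the exposure depends on a single recall, and on the person still being there to give it.

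Four stronger readings are tempting, and the protocol does not support them:
- *That events are in fact under-ascertained.* Nothing in the protocol measures this. Only a risk of late, misdated or missed events can be stated.
- *That 34 people will never be asked about app use.* That is a ceiling, since the timing of loss is not given. Some who leave early may be interviewed about their reasons, although that is not adverse event enquiry.
- *That safety during app use is unattended.* The care co-ordinator and risk-disclosure routes are in place and bear most on serious harm. They are reactive, however, and do not elicit other events.
- *That the comparison between arms is biased.* The schedule is the same in both arms, so the timing rule alone does not show bias.

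The remedy also has limits. Contacts may be by text or email, so they are not ready-made interviews and replies need checking. People who have disengaged may not answer. The project officer receives the allocation (5.0, Randomisation Process), so the person asking may be unblinded. These points shape the remedy but do not remove the case for it.

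**Conclusion.** The point holds as a modest design weakness that is cheap to improve. Systematic enquiry is confined to visits up to 12 weeks apart, and five contacts already made with every participant during app use are not used for it. Events outside the reactive safety routes therefore rest on one retrospective enquiry at week 12, and early losses, between 0 and about 34 of 170, have none covering their app use. The gap arithmetic assumes that contacts and visits are counted from the same start. No amount of under-capture and no loss of power should be claimed from the protocol. The matter belongs in the protocol, because when adverse events are asked about is trial conduct and 7.0 already fixes it.

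**What to change.** Add one scripted adverse event question, worded identically in both arms, to the contacts at weeks 1, 2, 4, 8 and 11, by whichever of phone, text or email the participant has chosen. Follow up a positive reply by phone and log it through the existing adverse event route. Name these contacts in 7.0 as enquiry times.

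Keep the enquiry at the visits, where follow-up assessments are done by blind research assistants. Report events found at contacts separately from those elicited at visits, because the caller may know the allocation. Do not pass details obtained at contacts to the research assistant who rates the follow-up PANSS.

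The cost is a little staff time at contacts that already take place, plus someone to check text and email replies. The downside is some ascertainment by a possibly unblinded caller. The script standardises the question but not all of the probing, hence the separate reporting.
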